A sample of 28 subjects provides at least 80% power for testing our primary endpoint in a non-inferiority framework comparing the exercise-enabled MPC algorithm with missed meal insulin detection to use of participant's personal closed loop system. Assumptions informing this calculation were derived from simulations showing an expected mean percent time in range (70-180 mg/dL) for control IQ that was 3.7% lower (as a difference rather than a ratio) and standard deviations (SDs) for the two conditions of approximately 16 to 19. From this, we assume the SD of the within-subject difference will be approximately 17% and use a one-sided paired t test at the 0.025 level of significance for a mean difference of 3.7% time in range versus 6% as the non-inferiority margin. We plan to recruit up to 36 subjects with goal enrollment of 30 subjects (about 15 at each center).

Protocol Summary:

Participants will undergo one 7-day Intervention Period and one 7-day Control Period in randomized order. During the 7-day intervention study, participants will wear an Omnipod to deliver Fiasp insulin and a Dexcom G6 CGM. The CGM system will provide sensed glucose data every 5 minutes. Sensed glucose data will be wirelessly transmitted via Bluetooth Low Energy (BTLE) from the Dexcom G6 transmitter to the smartphone master controller every five minutes. The smartphone will wirelessly communicate via BTLE to an Omnipod through a Personal Diabetes Manager (Insulet Corp.). The closed-loop system will receive activity data through a Polar M600 watch worn by the participant. Participants will eat one meal in clinic and complete system training on Day 1 and then spend the rest of the 7 days at home. During the 7-day Control Period, the participant will continue their usual diabetes care regimen using a t:slim X2 pump with Control IQ enabled or the Omnipod 5 closed loop system.

Participant Criteria

Inclusion Criteria:

1. Diagnosis of type 1 diabetes mellitus for at least 1 year.
2. Age 18 years and older.
3. Current use of a t:slim X2 insulin pump with the use of Control IQ or the Omnipod 5 system with closed loop enabled with Dexcom G6 or G7 for at least 12 weeks.
4. Willingness to use Fiasp insulin during intervention study
5. Lives with another person age 18 or older who will sleep in the house at night and that can attend the training on using the system.

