breast and pelvic exams. Females of child-bearing potential will take a urine pregnancy test, which must be negative to participate. A venous blood sample will be taken for the following tests: hemoglobin A1C, complete blood count, and complete metabolic set (including creatinine, liver set, and electrolytes). A study investigator will assess inclusion/exclusion criteria and review the participant's medical record for clarification as needed. When feasible, the participant's insulin pump and glucose sensor, if applicable, will be downloaded before enrollment to obtain the prior 4 weeks of data. A three-digit participant ID number will be assigned to the participant. This visit will take approximately 1.5 hours.

The treatment order will be randomized. The two periods, which are the 7-Day Control Period and 7-Day Intervention Period, will be a minimum of 7 days and a maximum of 8 weeks apart counting from the first day of the first period to the first day of the second period.

A complete list of times when participants will be instructed to take SMBG readings is listed below.

Participants will be instructed to take SMBG readings under the following conditions:

1. If the sensor glucose is $<70\text{mg/dL}$, the system will prompt a SMBG be entered. (intervention period only)
2. If the sensor glucose is $\geq 300\text{ mg/dl}$ for 30 minutes within the last 45 minute period, the system will prompt a SMBG be entered. (intervention period only)
3. If participant's symptoms (such as symptoms of hypoglycemia or hyperglycemia) are discrepant with the Dexcom CGM reading, then the participants will be instructed to perform a SMBG and use this value to make treatment decisions and to calibrate the Dexcom device. (Intervention and control period)
4. If CGM value is unavailable, a SMBG will be required to calculate a correction bolus. (Intervention and control period)
5. Before driving to clinic for study visits. (Intervention and control period)
6. On arrival to clinic for study visits. (Intervention and control period)
7. Before and after exercise if they choose to exercise during the study period. (Intervention and control period)
8. On discharge from clinic for study visits. (Intervention period)

7-Day Control Period

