The primary study endpoint is percent of time in range defined as glucose measured by Dexcom G6 or G7 in the range of 70-180 mg/dL. The hypothesis to be tested is if the MPC exercise-enabled closed-loop system with missed mealtime insulin algorithm will be non-inferior as compared to the participant's personal closed loop system. As our main approach, we will perform a two-sided Wilcoxon test for the paired differences. This test is widely used and easily interpreted. However, it cannot accommodate missing data or estimate crossover effects, and while we do not anticipate that these will affect our study outcomes, we plan to conduct a supplemental analysis using a linear regression model with bootstrapped standard errors, which do not require distributional assumptions. In resampling for the bootstrap, we will use study subjects as the sampling unit to account for correlation between their repeated observations. The general model is as follows:

$$(1) \quad Y_{ij} = \beta_0 + \beta_1 Trt_j + \beta_2 Seq_i + \beta_3 Period_j$$

In this model, the outcome Y_{ij} is the percent of time with sensed glucose 70-180 mg/dL for person i in observation period j . Trt_j represents the treatment arm (MPC=1, Control IQ=0). Seq_i is an indicator for sequence (AB vs BA) and $Period_j$ indicates when Trt_j occurred in the sequence. The coefficient β_0 represents the mean response for Control IQ, and the coefficient β_1 represents the difference between treatments to be tested. The coefficients β_2 and β_3 , mean differences for sequence or period, are both expected to equal zero; a large effect or significance test with p-value <0.05 will be considered evidence of a carryover effect. Hypothesis tests will be two-sided with type I error set to 0.05. Because statistical tests are specified and prioritized *a priori* and our proposed endpoints are highly related, we will follow recommendations to report p-values and confidence intervals rather than adjust for multiple comparisons.

Model fit and alternatives: Goodness of fit statistics and model fitting diagnostics will be used to assess for influential points and to evaluate alternative model specifications. If needed to compensate for some skew and heteroscedasticity in secondary outcomes, we will use bootstrapped variance estimators and compare these against robust estimates.

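### A significant period coefficient in the supplemental regression is to be read as carryover, which it cannot show; the sequence coefficient is too weak a test to settle the question

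*Protocol*

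**What the plan says.** The main analysis of time in range is a Wilcoxon test on paired differences. Because that test cannot estimate crossover effects, the protocol adds a regression: "we plan to conduct a supplemental analysis using a linear regression model with bootstrapped standard errors". Its terms are treatment (β1), sequence (β2) and period (β3).

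Of β2 and β3 the Statistical methods section says that they, as "mean differences for sequence or period, are both expected to equal zero", and then gives the rule: "a large effect or significance test with p-value <0.05 will be considered evidence of a carryover effect". The rule covers both coefficients without separating them and does not define a large effect. No action follows if it is met. On the level of the tests: "Hypothesis tests will be two-sided with type I error set to 0.05".

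The Screening (Visit 1) section sets the spacing of the two 7-day periods from start to start. They "will be a minimum of 7 days and a maximum of 8 weeks apart counting from the first day of the first period".

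**The concern.** In a two-period, two-sequence crossover the two coefficients answer different questions. β3 is the change from the first period to the second that both sequences share, such as learning, season or the effect of being observed. β1 is adjusted for it. β2 compares participants randomized to one order with those randomized to the other. It is the term aliased with differential carryover, but it is a between-subject contrast and is also confounded with chance group differences and treatment-by-period interaction.

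A rule that reads either coefficient as carryover can fail in two ways. An ordinary period effect would be reported as carryover and cast doubt on a sound treatment estimate. Non-significant coefficients would be taken to show that carryover is absent, when the test had little chance of finding it. This matters more because the regression is the only carryover check the protocol states, and because the minimum spacing lets the second period begin as the first ends (7 days from start to start, less a 7-day period, leaves 0 days).

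**Working it through.** **Inputs from the protocol's Power Analysis.** N = 28; SDs of the two conditions about 16 and 19; for the difference, "we assume the SD of the within-subject difference will be approximately 17" percentage points; expected advantage of the new system 3.7 points; margin 6 points.

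**Assumptions.** 14 participants per sequence (the protocol says only that order is randomized) and normal-theory tests in place of the bootstrap.

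**The protocol's own figure first.** It says "A sample of 28 subjects provides at least 80% power for testing our primary endpoint in a non-inferiority framework", and to get there "use a one-sided paired t test at the 0.025 level of significance". The distance to the margin is 3.7 + 6 = 9.7, and the standard error is 17/√28 = 3.21. The noncentral t distribution gives 82.9% power at n = 28, and 80% needs n = 27. The figure reproduces, so the SD inputs can be used for the rest.

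**Standard errors of the two coefficients.**
- Within-subject correlation: (16² + 19² − 17²)/(2 × 16 × 19) = 328/608 = 0.54.
- SD of a participant's two-period total: √(16² + 19² + 328) = √945 = 30.74, where 328 is twice the covariance; SD of the two-period mean, half of that, 15.37.
- SE of the sequence contrast: 15.37 × √(2/14) = 5.81.
- SE of the period coefficient: (17/2) × √(2/14) = 3.21.
- Both tests have 26 degrees of freedom, two-sided 0.05.

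**What each effect does to the estimates.** Let a period shift be P, and let carryover of size L run from the new system into a following Control Period only. The mean within-subject difference (new system minus control) is τ − P − L when the new system comes first and τ + P when it comes second.
- Treatment estimate, the average of the two: τ − L/2. P cancels.
- Period coefficient, half the second minus the first: P + L/2.
- Sequence contrast: L/2.

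The period coefficient therefore mixes P and L/2 and cannot tell them apart.

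**False alarms (L = 0).**
- P = 5: the period test is significant 32% of the time. P = 7: 55%. In simulation at P = 5 the treatment estimate stayed unbiased.
- P = 0: at least one of two independent tests fires with probability 1 − 0.95² = 9.75%.

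**Detection of real carryover.**

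| L (points) | Treatment bias L/2 | Sequence test | Period test | Either test |
|---|---|---|---|---|
| 6 | 3 | 8% | 15% | 21–22% |
| 12 | 6 | 17% | 44% | 51–55% |

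The last two columns are for one-sided carryover. The range in the last column depends on which arm has the larger SD, which the protocol does not state; I checked it by simulating both assignments. The sequence test reaches 80% power only at L of about 34 points. With both SDs at 16 its power at L = 12 is 20%, and with both at 19 it is 15%.

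The extra flags in the last column come from the period test. With L = 12 the period coefficient moves by 6 points. A plain 6-point period shift without carryover moves it by the same amount and is flagged by that test equally often, 44%.

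**The case against.** Three objections carry weight.

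**The period coefficient is not blind to carryover.** The Control Period continues the closed-loop system the participant has already used for at least 12 weeks, so any carryover would plausibly run one way, from the new system into control. Such carryover moves β3 by half its size. A reader might infer that the period term carries no information on carryover; that is too strong. What stands is that a significant β3 cannot be attributed to it.

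**The rule flags on either coefficient.** A reader might take 8% and 17% as the detection rate of the whole rule and conclude that real carryover would almost always be missed. Those figures are for the sequence test alone. Under the rule as written, one-sided carryover of 12 points is flagged about half the time, and the undefined large-effect clause could add more. This does not rescue the rule, since the added flags are indistinguishable from a harmless period effect.

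**Little depends on it.** A reader might infer that the primary conclusion is at risk from this rule. The documents do not support that: the main test is the Wilcoxon, the regression is supplemental, and no model switch or discarding of data follows from a flag. The protocol also already commits to reporting p-values and confidence intervals.

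In addition, the effect sizes used here are illustrative; nothing in the protocol suggests a particular period shift or carryover. Seven days is the minimum spacing only, and up to 8 weeks is allowed, so the text permits back-to-back periods without making them the norm.

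**Conclusion.** The rule is wrong as written for the period coefficient and unreliable for the sequence coefficient. A pure period shift of 5 to 7 points would be labelled carryover by the period test in about a third to over half of trials while the treatment estimate stays unbiased. Carryover large enough to bias the treatment difference by the full 6 points used for power would be picked up by the sequence test about one time in six. The Study Hypothesis gives the margin as 7%; a 7-point bias (L = 14) would be detected about 21% of the time, so that separate inconsistency does not change the conclusion.

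The figures rest on the protocol's SDs, an assumed 14/14 split and normal-theory tests; 15 per sequence raises the sequence test's power at L = 6 and L = 12 by about one point or less. The algebra needs none of these sizes. The consequence is confined to interpretation of the supplemental model, but the correction is worth making because the protocol prescribes a wrong inference.

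**What to change.** In the Statistical methods section:

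- Delete the sentence that treats a large or significant β2 or β3 as evidence of carryover, together with the undefined large-effect criterion.
- Say that, in the supplemental model, β3 is a nuisance adjustment for period and is not interpreted as carryover.
- Say that β2 is reported with its confidence interval, without a p < 0.05 decision about carryover, and that a non-significant value is not taken as evidence of no carryover.
- Argue from the design why carryover is expected to be negligible, acknowledging that 7-day periods may start 7 days apart.

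Optionally, add a sensitivity run that leaves out the first 24 hours of CGM in each period. It would address short-lived carryover only. Carryover confined to day 1 would need to be 6 × 7 = 42 points of time in range on that day to move the 7-day mean by 6 points, and longer-lasting carryover would survive the cut.

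The cost is a few sentences, plus one re-run of existing data if the sensitivity analysis is adopted. No new data are needed. The wording should be fixed before results are seen.

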- Requires medical or surgical intervention to prevent permanent impairment or damage

Exceptions to the SAE definition will include the following:

- Elective surgery
- A planned hospitalization for pre-existing condition, without a serious deterioration in health

Any SAE, including death, due to any cause (related or unrelated to the device), that may occur during a clinical study will be reported to the PI and Medical Monitor immediately (within 1 working day of learning of the event).

Severity of Adverse Events

The following definitions may be used to rate severity of AEs:

- **Mild**

Awareness of signs or symptoms, but easily tolerated; are of minor irritant type that is outside the norm for the disease state or subject; causing no loss of time from normal activities; symptoms would not require medication or a medical evaluation; signs and symptoms are transient. Mild hypoglycemia is expected in diabetes and will not be captured as an AE.

***Example:** ketosis not requiring an ER visit.*

- **Moderate**

Discomfort severe enough to cause interference with usual activities, requiring treatment by family member or emergency personnel

Example: infusion site infection requiring antibiotics prescribed at urgent care.

- **Severe**

Incapacitating, causing inability to do work or usual activities; signs and symptoms may be of systemic nature or require medical evaluation and/or treatment at a health care facility

Example: severe hypoglycemia defined as hypoglycemic event resulting in altered consciousness requiring another person to actively administer carbohydrate, glucagon, or other resuscitative actions.

Relationship of Adverse Events to Study or Study Device

The investigator will categorize the relationship of the event to the study or study device as follows:

- **Not Related**

AE is due to an underlying disease state or concomitant medication or therapy not related to the device, disease or study.

- **Unlikely Related**

AE has minimum or no temporal relationship to the study device, disease or study participation and/or a more likely alternative etiology exists.

- **Possibly Related**

AE has a strong temporal relationship to the study device, disease or study procedures and alternative etiology is equally or less likely compared to the potential relationship to the device, disease or study.

- **Probably Related**

AE has a strong temporal relationship to the study device, disease or study and another etiology is unlikely.

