- **Definitely Related**

AE has a strong temporal relationship to the study device, study procedures or disease and another etiology does not exist.

Unanticipated Problems

Unanticipated problems, including study, disease or device-related problems will be detected by reviewing descriptions of known or foreseeable adverse events and risks in the IRB-approved research protocol and the current IRB approved consent form, any underlying disease or conditions of the subject experiencing the adverse event, a careful assessment of whether the adverse event is related or possibly related to the subject's participation in the study or if root cause or associations is with study devices.

Unanticipated Adverse Device Effect (UADE)

An unanticipated adverse device effect (UADE) is not expected to occur. An UADE is defined as any serious adverse effect on health or safety or any life-threatening problem or death caused by – or associated with – the device, if that effect, problem, or death was not previously identified in nature, severity, or degree of incidence in the investigational plan (including documents such as the protocol, the informed consent document, other study-related documents), or any other unanticipated serious problem associated with the device that relates to the rights, safety, or welfare of participants.

During the review of a reported SAE, if the PI and Medical Monitor input determines the severity or extent of the event was not cited in this protocol or associated protocol materials, and the event was classified as, ‘possibly related’ to the device, the event will be documented as an UADE. If the event is classified as an UADE, the Investigator must notify the IRB and the FDA within ten (10) working days of the original SAE notification.

If determined that the UADE presents an unreasonable risk to participants, we will terminate all investigations or parts of investigations presenting that risk as soon as possible, but not later than 5 working days after such determination is made and not later than 15 working days after we first receives notice of the original SAE. We will not resume a terminated study without IRB and FDA approval.

Medical Device Reporting (MDR)

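### The working UADE rule names one of three positive relatedness levels, so it is narrower than the protocol's own UADE definition

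*Protocol*

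**What the plan says.** Under Relationship of Adverse Events to Study or Study Device, the protocol introduces its scale with "The investigator will categorize the relationship of the event to the study or study device as follows". It then lists five separately labelled levels: not, unlikely, possibly, probably and definitely related. The two strongest differ in how far other causes are ruled out:

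- The second strongest level, probably, asks for close timing and leaves room for a different cause only if that cause is improbable.
- For the strongest level, definitely, the text is "AE has a strong temporal relationship to the study device, study procedures or disease and another etiology does not exist".

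The UADE section then makes three statements in sequence.

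1. Definition. A UADE is "any serious adverse effect on health or safety or any life-threatening problem or death caused by – or associated with – the device", provided that the effect was not already identified in the investigational plan. No relatedness level is named.
2. Working rule. When an SAE is reviewed, two conditions must be met. The PI, with Medical Monitor input, "determines the severity or extent of the event was not cited in this protocol or associated protocol materials", and the relatedness condition is satisfied: "the event was classified as, ‘possibly related’ to the device, the event will be documented as an UADE".
3. Consequence. "If the event is classified as an UADE, the Investigator must notify the IRB and the FDA within ten (10) working days", counted from the original SAE notification. If the UADE is judged an unreasonable risk, the affected investigations end within 5 working days of that decision and within 15 working days of the first notice of the SAE. They restart only with IRB and FDA approval.

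**The concern.** The working rule is the sentence staff apply to a reported SAE. It puts one scale label in quotation marks. It does not say *at least* possibly related, and it does not mention the two stronger levels. An unforeseen serious event with a weaker device link therefore meets the condition, while one rated definitely related does not meet it as worded. That ordering cannot be intended.

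At stake is the step that starts the UADE clock. The 10 working days run from the original SAE notification, so time spent settling whether the rule or the definition governs comes out of the reporting window. With two sites, the sentence may also be read in two ways.

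**Working it through.** There is no plan figure to reproduce, and the only arithmetic is a count. The check sets the scale against the two UADE sentences, then asks which reporting routes depend on the rule.

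**Step 1: scale against definition and rule.** Assume an SAE that the study materials did not foresee.

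| Level | Distinguishing test | Within the definition? | Named in the rule? |
|---|---|---|---|
| Not related | due to something other than device, disease or study | no | no |
| Unlikely | little or no temporal link, and/or a more likely alternative | not normally | no |
| Possibly | strong temporal link; alternative no more likely than the device | yes | yes |
| Probably | strong temporal link; alternative unlikely | yes | no |
| Definitely | strong temporal link; no alternative | yes | no |

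The definition reaches three positive levels and the rule names one, which leaves 3 − 1 = 2 without an instruction.

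**Step 2: which reports depend on the rule?**

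| Route and section | Recipient | Depends on the UADE rule? | Scope |
|---|---|---|---|
| Serious Adverse Events | PI and Medical Monitor, 1 working day | no | every SAE, related or not |
| Safety Oversight | DSMB, when the event occurs | no | all device-related SAEs, besides all UADEs |
| Adverse Event Reporting | IRB, 5 calendar days | no | reportable new information; no relatedness level named |
| Entire study stopping rules, and Safety assessment – first 5 participants | FDA, with a halt | no | severe hypoglycemia and diabetic ketoacidosis |
| Entire study stopping rules | pause until the root cause is evaluated; no FDA notice stated in that sentence | no | unexpected events such as death or hospitalization |
| Risks and Benefits | FDA and sensor company | no | sensor breakage |
| Medical Device Reporting | manufacturers of the marketed CGM and pump | no | those devices; the study's control algorithm is not mentioned |
| UADE section | IRB and FDA, 10 working days; termination pathway | yes, through UADE classification | unanticipated device-related SAEs in general |

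**Step 3: what is left.** Remove every event that reaches FDA by another route. The remainder is an unforeseen SAE, rated probably or definitely device-related, that is neither severe hypoglycemia, nor ketoacidosis, nor sensor breakage. For these events the UADE section is the only general FDA route in the protocol.

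**Step 4: a second mismatch in the same sentence.** The definition calls an event unanticipated if its nature, severity or degree of incidence was not identified beforehand. The rule tests severity or extent only. This is minor, but it can be settled in the same edit.

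**The case against.** The strongest reply is that the rule sets a floor. It does not say *only*. The wording for possibly related, under which an alternative cause is no more likely than the device, is also satisfied by events at the two stronger levels. The Unanticipated Problems paragraph just above speaks of events that are related or possibly related, which uses possibly as the lower bound. Notification follows from classification as a UADE, and the definition already makes a definitely related event a UADE. The protocol also binds the investigator to current FDA regulations.

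Much of this stands. The floor reading is plausible and probably what was meant. But the scale treats the levels as separate categories, the rule quotes one label, and the neighbouring paragraph shows that the authors could name both when they meant both. A reporting rule should not need its readers to repair it by inference.

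A reader might go further and infer that the most clearly device-related serious events drop out of safety reporting, including notice to the DSMB. The protocol does not support that. Safety Oversight sends all device-related SAEs to the DSMB as they occur, whether or not they are labelled UADEs. The IRB route for new information names no relatedness level. Severe hypoglycemia and ketoacidosis halt the study and go to FDA whatever their rating. Nor are the stronger levels clearly outside the notification trigger, since the definition still includes them. The two sentences conflict, and neither is stated to prevail.

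**Conclusion.** The point holds as a drafting conflict with a narrow but real consequence. The working rule names one of the three positive levels and is narrower than the definition it is meant to apply. Read literally, it does not direct that an unforeseen SAE rated probably or definitely device-related be documented as a UADE. What this exposes is the notice "the Investigator must notify the IRB and the FDA within ten (10) working days of the original SAE notification", as it concerns FDA, together with the UADE termination pathway, for events without another FDA route.

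Two of three is a count of labels and does not estimate missed reports. The protocol does not expect a UADE, and the investigational exposure is small: up to 36 participants for 7 days, or 36 × 7 = 252 participant-days, not counting repeated visits. The number of affected events is likely to be very low and may be zero. The case for correction is that the rule should not be weakest where the device link is strongest.

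The conclusion assumes that staff apply the working sentence as written, and that no separate safety document shown to them states the rule more fully. Nothing in the endpoint, sample size or analysis changes.

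**What to change.** In the UADE section, reword the relatedness condition so that it covers an event *classified as possibly, probably or definitely related to the device*. In the same edit, match the rule's test of what is unanticipated to the three attributes in the definition.

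The cost is a few words in a protocol amendment. No new data, form or analysis is needed, and there is no apparent downside: the definition already counts these events as UADEs.
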